**Figure 9: Adjudication of AEs**

### 13.3.2 DSB REPORTING

All SAEs meeting the definition of unanticipated problem as stated in Section 13.3.1 will be reported to DSMB within 24-48 hours of investigator/coordinator awareness of the event. For all other AEs meeting the definition of unanticipated problem a written report will be sent to the DSMB within 10 working days. The DSMB will also review all AE and clinical outcomes during regularly scheduled meetings and at the final analyses, including frequency of rescue procedures and hypotension in all the study groups. If the DSMB determines that

the overall rate of adverse events is higher in any of the two intervention groups, University of Pittsburgh HRPO will be notified within 15 days of this determination. An AE table summarizing IRB and DSMB reporting timeline is provided below.

**Table 7: Reporting timelines**

Reporting organization	Fatal or life-threatening AE meeting definition of unanticipated problem	All other AEs meeting definition of unanticipated problem	AEs that are expected and listed as secondary or safety outcome
Co-ordinating center	24 hours	5 working days	No reporting
IRB	24 hours	10 working days	No reporting
DSMB	24-48 hours	10 working days	Reporting at the regular DSMB meeting

## 14 APPENDICES

### A. CALCULATION OF NIH GENDER-SPECIFIC PREDICTED BODY WEIGHT

Predicted body weight (PBW) is calculated from gender and height (heel to crown) according to the following equations:

Males: PBW (Kilograms) =  $50 + 2.3 \times [\text{height (inches)} - 60]$

Females: PBW (Kilograms) =  $45.5 + 2.3 \times [\text{height (inches)} - 60]$

## B. KDIGO CRITERIA FOR DIAGNOSING AND STAGING OF ACUTE KIDNEY INJURY

### B1. DIAGNOSIS OF AKI

AKI will be diagnosed using as any of the following

- Increase in serum creatinine  $\geq 0.3$  mg/dL within 48 hoursa  
OR
- Increase in serum creatinine  $\geq 1.5$  times baseline, which is known or presumed to have occurred within prior 7 daysa  
OR
- Urine volume  $<0.5$  mL/kg/h for 6 hours  
OR
- Increase in serum creatinine value  $\geq$  the age, gender, and race corrected levels in Table B1

a The increase in serum creatinine (absolute and relative) will be determined based on the lowest available serum creatinine value in the past 12 months. If no baseline value is available, AKI status will be determined using the age- and gender-corrected table below provided there is no past medical history of chronic kidney disease

**Table B1:** Cut-off values for serum creatinine based on 1.5 times estimated normal values for age group

Age (years)	Black Male mg/dL	Other Male mg/dL	Black Female mg/dL	Other Female mg/dL
20-24	2.3	2.0	1.8	1.5
25-29	2.3	1.8	1.7	1.5
30-39	2.1	1.8	1.7	1.4
40-54	2.0	1.7	1.5	1.4
55-65	2.0	1.7	1.5	1.2
>65	1.8	1.5	1.4	1.2

### B2 STAGING OF AKI

**Table B2:** Determination of the stage of AKI

Stage	Serum Creatinine	Urine Output
1	1.5 – 1.9 times baseline OR $\geq 0.3$ mg/dl increase	<0.5 mL/kg/h for 6 – 12 hours
2	1.0 – 2.9 times baseline	<0.5 mL/kg/h for $\geq 12$ hours
3	3.0 times baseline OR Increase in serum creatinine to $\geq 4.0$ mg/dl OR Initiation of kidney replacement therapy	<0.3 mL/kg/h for 24 hours OR Anuria $\geq 12$ hours

## C. DEIDENTIFIED DATA ELEMENTS FOR SCREENED, NON-ENROLLED SUBJECTS

The following data elements will be collected on screened subjects who met the inclusion criteria but were not enrolled.

- Has CKRT been started?
- Was UFNET commenced before screening?
- Was the attending intensivist/nephrologist intending to start CKRT for fluid removal?
- Month of year that patient met screening criteria (02-21)
- Gender
- Ethnicity
- Age (if age >89, 89 will be entered as age)
- Patient location (e.g., TICU, Medical ICU etc.) and if regularly screened
- Reason(s) patient excluded from study
- If not excluded, not enrolled, why?
- Cause of acute kidney injury

#### D. CONTINUOUS KIDNEY REPLACEMENT THERAPY (CKRT) MANAGEMENT PROCEDURES

General treatment parameters for the prescription of CKRT are summarized in the table below.

Modality	CVVHDF, CVVHD, CVVH, or SCUF
Treatment schedule	Continuous
Hemofilter	M100 or any synthetic hollow-fiber membranes
Blood flow rate	200 – 350 mL/min, prescribed by primary team
Effluent flow rate	20-30 mL/kg/h
Dialysate	Bicarbonate buffered; electrolyte composition prescribed by primary team
Dialysate flow rate	Prescribed by primary team
Post-filter replacement fluid	Bicarbonate buffered; electrolyte composition prescribed by primary team
Pre-filter replacement fluid	Bicarbonate buffered; electrolyte composition prescribed by primary team
Ultrafiltration rate	As per study protocol
Anticoagulation	Prescribed by primary team
System change	At least every 48-72 hours

To deliver the targeted dose of  $UF_{NET}$ , it is critical that periods of time during which the patient is off CKRT are kept as brief as possible. We recognize that patients will need to come off therapy for a variety of reasons, including CT scans, MRI scans, angiographic and surgical procedures. The ICU staff will be educated as to the importance of resuming treatment promptly upon the patients return to the ICU. Similarly, when systems need to be changed, either due to system clotting, or due to routine system changes, the time off therapy needs to be minimized.

## E. SOFA SCORING SYSTEM

Variables	Sequential Organ Failure Assessment Score				
	0	1	2	3	4
Respiratory					
PaO 2 /FiO 2 (mmHg)	>400	≤400	≤300	≤200 a	≤100 a
Coagulation					
Platelets (x 10  /µL)	>150	≤150	≤100	≤50	≤20
Liver					
Bilirubin	<1.2	1.2 – 1.9	2.0 – 5.9	6.0 – 11.9	>12.0
Cardiovascular					
MAP (mmHg)	≥70	<70			
Vasopressor b (doses in mcg/kg/min)			Dopamine ≤5 OR Dobutamine (any dose)	Dopamine >5 OR Epinephrine ≤0.1 OR Norepinephrine ≤0.1	Dopamine >15 OR Epinephrine >0.1 OR Norepinephrine >0.1
	None	None			
Central Nervous System					
Glasgow Coma Scale	15	13 – 14	10 – 12	6 – 9	<6
Kidney					
Creatinine (mg/dL)	<1.2	1.2 – 1.9	2.0 – 3.4	3.5 – 4.9 OR <500	≥5 OR <200
Urine output (mL/day)					

a Values are with ventilatory support; the maximum score in patients not receiving ventilatory support is 2

b Pressor agents administered for at least 1 hour

We define a clinically significant organ failure as a new SOFA score of ≥2

## F. TIME-EVENTS SCHEDULE

### F1. GENERAL DATA COLLECTION

Measurement/Event	Screening	Baseline/ Day 0@	1	2	3	4	5	6	7	8- 14	15- 21	22- 28
Serum Creatinine	X	X	X	X	X	X	X	X	X	X	X	X
Demographics, History and Physical		X										
AKI Cerner alerts	X	X										
Etiology of AKI		X										
APACHE II		X										
Weight*		X	X	X	X	X	X	X	X	X	X	X
Daily FB*		X	X	X	X	X	X	X	X	X	X	X
Restrictive UF NET		X	X	X	X	X	X	X	X	X	X	X
Liberal UF NET		X	X	X	X	X	X	X	X	X	X	X
Ventilator parameters ΦΨ*		X	X	X	X	X	X	X	X	X	X	X
CKRT parameters ΦΨ\$		X	X	X	X	X	X	X	X	X	X	X
ABG*		A	A	A	A	A	A	A	A	A	A	A
Fluids (intake/output)*		X	X	X	X	X	X	X	X	X	X	X
MAP*		X	X	X	X	X	X	X	X	X	X	X
CVP, CI, PPV, SVV, and other hemodynamic data*		A	A	A	A	A	A	A	A	A	A	A
Hypotensive & Hypertensive episodes \$%		X	X	X	X	X	X	X	X	X	X	X
Cardiac arrhythmias \$%		X	X	X	X	X	X	X	X	X	X	X
Use of rescue UF NET rates \$		X	X	X	X	X	X	X	X	X	X	X
Severe hypophosphatemia\$		X	X	X	X	X	X	X	X	X	X	X
Severe hypokalemia\$		X	X	X	X	X	X	X	X	X	X	X
Severe hypocalcemia		X	X	X	X	X	X	X	X	X	X	X
All lab data*		X	X	X	X	X	X	X	X	X	X	X
Vital signs and medications*		X	X	X	X	X	X	X	X	X	X	X
Inability to close surgical wounds		X	X	X	X	X	X	X	X	X	X	X
New organ dysfunction*		X	X	X	X	X	X	X	X	X	X	X
Secondary infections		X	X	X	X	X	X	X	X	X	X	X
SOFA score β*	X	X	X	X	X	X	X	X	X	X	X	X
Vital status		X	X	X	X	X	X	X	X	X	X	X

Measurement/Event	Screening	Baseline/ Day 0@	1	2	3	4	5	6	7	8- 14	15- 21	22- 28
KRT Status		X	X	X	X	X	X	X	X	X	X	X
IHD use			X	X	X	X	X	X	X	X	X	X

X= Required

A=When available

Ψ=Data gathered at times indicated or until 72 hours, whichever occurs first

β=Records clinically available creatinine, platelets, bilirubin, MAP, SBP, FiO2, fluid bolus and vasopressor use

ϕ=Measure during reference period (0600 -1000); other values may be obtained closest to 0800 on the specified calendar date

\* = collected only if the patient is still in the ICU before day 28 and if available in the electronic health records

\$\_= collected only if the patient is on CKRT upto 24 hours following discontinuation of CKRT

%=collected only if the patient is on IHD

@ =Data collected before initiation of study intervention

## F2. CKRT DATA COLLECTION

Measurement/ Event	Initiation of RRT	Baselin e/Day 0@	1	2	3	4	5	6	7	8-14	15-21	22-28
Indication for KRT - Volume status - Serum potassium - Acid-base status - Symptoms - BUN - Hemodynamic status	X											
CKRT - Mode - Hemodiafilter - Blood flow rate - Dialysate flow rate - Replacement fluid rate - Ultrafiltration rate - Net Ultrafiltration rate - Hours of therapy - 24- hour effluent volume - Anticoagulation		X	X	X	X	X	X	X	X	X	X	X
Complications - Clogging - Clotting - Downtime		X	X	X	X	X	X	X	X	X	X	X

Measurement/ Event	Initiation of RRT	Baseline e/Day 0@	1	2	3	4	5	6	7	8-14	15-21	22-28
- Discontinuation of UF NET due to patient instability												
Indications for termination of KRT		X	X	X	X	X	X	X	X	X	X	X

@= Data collected before initiation of study intervention

## G. ADVERSE EVENT REPORTING AND UNANTICIPATED PROBLEMS

### G1. DETERMINING RELATIONSHIP OF ADVERSE EVENTS TO STUDY PROCEDURES

Investigators will be asked to grade the strength of the relationship of an adverse event to study procedures as follows:

- Definitely Related: The event follows: a) A reasonable, temporal sequence from a study procedure; and b) cannot be explained by the known characteristics of the patient's clinical state or other therapies; and c) evaluation of the patient's clinical state indicates to the investigator that the experience is definitely related to study procedures.
- Probably or Possibly Related: The event should be assessed following the same criteria for "Definitely Associated". If in the investigator's opinion at least one or more of the criteria are not present, then "probably" or "possibly" associated should be selected.
- Probably Not Related: The event occurred while the patient was on the study but can reasonably be explained by the known characteristics of the patient's clinical state or other therapies.
- Definitely Not Related: The event is definitely produced by the patient's clinical state or by other modes of therapy administered to the patient.
- Uncertain Relationship: The event does not meet any of the criteria previously outlined.

### G2. UNANTICIPATED PROBLEMS (UP)

Investigator will report Unanticipated Problems, regardless of severity, associated with the study procedures to University of Pittsburgh HRPO and DSMB. An unanticipated problem is defined as follows: any incident, experience, or outcome that meets all the following criteria:

- Unexpected, in terms of nature, severity, or frequency, given the research procedures that are described in the protocol-related documents, such as the HRPO-approved research protocol and informed consent document; and the characteristics of the subject population being studied.
- Related or possibly related to participation in the research. Possibly related means there is a reasonable possibility that the incident, experience, or outcome may have been caused by the procedures involved in the research.
- Suggests that the research places subjects or others at a greater risk of harm (including physical, psychological, economic, or social harm) than was previously known or recognized.

## H. DATA AND SAFETY MONITORING BOARD

The principal role of the DSMB is to assure the safety of patients in this feasibility trial. They will regularly monitor the data from this trial, review and assess the performance of its operations, and make recommendations to the Principal Investigator with respect to:

- Review of adverse events
- Possible modifications in the clinical trial protocol

The Clinical and Translational Science Institute at the University of Pittsburgh will appoint a DSMB. The DSMB will consist of members with expertise in critical care medicine, nephrology, and biostatistics. Appointment of all members is contingent upon the absence of any conflicts of interest. The Principal Investigator will be responsible for the preparation of all DSMB and adverse event reports.

The DSMB will review the protocol and sample consent form during its first meeting. Subsequent DSMB meetings will be scheduled in accordance with the DSMB. When appropriate, face-to-face (*i.e.*, Teams/Zoom) meetings will be held. Recommendations to end, modify, or continue the trial will be prepared by the DSMB executive secretary. Recommendations for major changes, such as stopping, will be reviewed by the DSMB and communicated immediately. Other recommendations will be distributed to the RELIEVE-AKI steering committee.

## I. COMMON REASONS FOR ACUTE KIDNEY INJURY, FLUID OVERLOAD AND RAPID UFNET

### I1. COMMON CAUSES FOR AKI AND FO

- Sepsis
- Massive hemorrhage
- Cardiac surgery
- Major trauma
- Acute pancreatitis

### I2. COMMON REASONS FOR RAPID UFNET

- Severe fluid overload with impending respiratory failure
- Acute heart failure with pulmonary edema and cardio-renal syndrome
- Refractory hypoxemia due to fluid overload and ARDS while on mechanical ventilation
- Severe fluid overload after massive septic shock resuscitation
- Chronic kidney disease and heart failure or COPD

## 2 STUDY OVERVIEW

This document is the Statistical Analysis Plan for the RELIEVE-AKI study. The document describes the statistical methods used to analyze the primary, secondary and safety outcomes in the study. Appendix A is a list of all variables that will be analyzed in the study along with their classification and analysis method. Appendix B is the definition of all derived and composite variables and the data imputation rules for all variables where imputation is used. Appendix C shows the shell tables.

## 3 TRIAL SUMMARY

The overall objective of RELIEVE-AKI randomized trial is to examine the feasibility of restrictive rate of net fluid removal (*i.e.*,  $UF_{NET}$ ) during treatment with continuous kidney replacement therapy (CKRT) among critically ill patients with acute kidney injury. Our central hypothesis is that a restrictive  $UF_{NET}$  rate strategy embracing a “slow and steady” approach to fluid removal is associated with fewer complications, including cardiac arrhythmias, hypotension, and death, compared with a more liberal “sprint and pause” strategy among critically ill patients.

The RELIEVE-AKI study is a prospective, two-center, unblinded, parallel-group, 2-arm, comparative effectiveness, stepped-wedge cluster-randomized trial (SW-CRT) among 144 critically ill patients with AKI treated with CKRT in 6 ICUs across two hospital systems. The trial will be conducted at 3 ICUs at University of Pittsburgh Medical Center in Pittsburgh, PA, as well as 3 ICUs at Mayo Clinic, Rochester, MN. ICUs will be randomized 1:1 to either a restrictive or a liberal  $UF_{NET}$  rate strategy. During the first five months, all ICUs will continue with a liberal  $UF_{NET}$  rate strategy. Every three months thereafter, one ICU will be randomized to deploy the restrictive  $UF_{NET}$  rate strategy. In the liberal group, the  $UF_{NET}$  rate will be titrated between 2.0-5.0 mL/kg/h and maintained throughout fluid removal. In the restrictive group, the  $UF_{NET}$  rate will be titrated between 0.5-1.5 mL/kg/h and maintained throughout fluid removal. The  $UF_{NET}$  rates used in both strategies are used in current clinical practice.

The primary feasibility outcomes are a.) between-group separation in mean delivered  $UF_{NET}$  rates of a minimum of 0.52 mL/kg/h; b.) protocol deviation defined as  $UF_{NET}$  rate out of range of >0.5 mL/kg/h lower or higher than the assigned  $UF_{NET}$  rate range for six consecutive hours; and c.) patient recruitment of two patients per month per each center. We will explore the effects of restrictive and liberal  $UF_{NET}$  rate groups on secondary outcomes such as daily and cumulative fluid balance, duration of kidney replacement therapy and mechanical ventilation, organ-failure free days, ICU and hospital length of stay, hospital mortality, and kidney replacement therapy dependence by hospital discharge.

We will also assess safety outcomes such as intradialytic hypotensive and hypertensive episodes; cardiac arrhythmias; emergent use of rescue  $UF_{NET}$  rates higher than the assigned group for treatment of fluid overload; severe hypophosphatemia, hypokalemia, and hypocalcemia; CKRT circuit downtime due to filter clotting or clogging; discontinuation of fluid removal due to hemodynamic instability; inability to close surgical wounds due to edema; new organ dysfunction; diastolic and systolic dysfunction; pulmonary edema; ileus, bowel ischemia, anastomotic break down; pressure ulceration; wound infections; arterial or venous thrombosis; severe anemia requiring red cell transfusion, severe thrombocytopenia requiring platelet transfusions; and secondary infections.

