We propose a prospective, two-center, unblinded, parallel-group, 2-arm, comparative effectiveness, stepped-wedge cluster-randomized trial among 112 critically ill patients with AKI treated with CKRT in 10 ICUs across two hospital systems. The trial will be conducted at 5 ICUs at University of Pittsburgh Medical Center in Pittsburgh, PA, as well as 5 ICUs at Mayo Clinic, Rochester, MN. ICUs will be randomized 1:1 to either a restrictive or a liberal UFNET rate strategy. During the first six months, all ICUs will continue with a liberal UFNET rate strategy. Thereafter, one ICU will be randomized to deploy the restrictive UFNET rate strategy using a rolling randomization strategy. In the liberal group, the UFNET rate will be titrated between 2.0-5.0 mL/kg/h and maintained throughout fluid removal. In the restrictive group, the UFNET rate will be titrated between 0.5-1.5 mL/kg/h and maintained throughout fluid removal. The UFNET rates used in both strategies are used in current clinical practice.

The primary feasibility outcomes are a.) between-group separation in mean delivered UFNET rates of a minimum of 0.53 mL/kg/h; b.) protocol deviation defined as UFNET rate out of range of >0.5 mL/kg/h lower or higher than the assigned UFNET rate range for six consecutive hours; and c.) patient recruitment of one patient per time window per ICU. We will explore the effects of restrictive and liberal UFNET rate groups on secondary outcomes such as daily and cumulative fluid balance, duration of kidney replacement therapy and mechanical ventilation, organ-failure free days, ICU and hospital length of stay, hospital mortality, and kidney replacement therapy dependence by hospital discharge.

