We chose the above metric for protocol deviation because with complex interventions, as the frequency of monitoring increases, so does the resources required to track protocol adherence. Close monitoring of protocol deviations is unlikely in trials that lack resources, introducing a risk of ascertainment bias. In contrast, with very frequent monitoring of continuous interventions, the likelihood of recording protocol deviations increases but the clinical impact of each deviation diminishes proportionately. Similarly, criteria for protocol deviations that are too sensitive would exaggerate the impact of protocol deviations beyond what is clinically important and unduly undermine the apparent feasibility and internal validity of the trial.

All reasons for non-adherence will be recorded for both groups using pretested taxonomy distinguishing clinical reasons (*e.g.*, hypotension, hypertension, difficulty in oxygenation, respiratory distress, hemodynamic instability, attending override of protocol) and research-related reasons (*e.g.*, consent withdrawal).

3. *Recruitment rate*: A successful recruitment rate will be defined as achieving an enrollment rate of 1 patient per ICU per time window during the trial. While this feasibility trial is ongoing, recruitment will be reviewed weekly; the screening records

will be reviewed monthly, and the numbers of missed eligible patients will be investigated. If applicable, we will discuss barriers to enrollment and use well-developed strategies to improve recruitment. Therefore, recruitment will be maximized as necessary over the course of the trial. The recruitment metric will be measured and interpreted at the end of the trial by calculating the mean number (standard deviation) of recruited patients per active screening month.

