### 6.3.2 RANDOMIZATION UNIT

Following best practice recommendations for evaluation of system-level interventions, the unit of randomization is the cluster (*e.g.*, ICU) rather than the individual patient. During the first six months of data collection, all sites will continue with a liberal UFNET rate strategy. Thereafter, one ICU will be randomized to deploy the restrictive UFNET rate strategy every two months or when a maximum of 10 patients have been enrolled, whichever occurs first, and stay in this strategy until the end of the study (Figure 6).

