### 3.2 EXCLUSION CRITERIA

1. Respiratory distress due to pulmonary edema or fluid overload
2. Massive volume infusion (*i.e.*,  $>200$  mL/h for  $>6$  hours of continuous infusion)
3. No intention to remove net fluid as determined by attending intensivist or nephrologist
4. Attending intensivist or nephrologist believes that the protocol will not be followed
5. Continuous net fluid removal for  $>24$  hours prior to study enrollment
6. Body Mass Index  $>40$
7. Patients on chronic outpatient hemodialysis
8. Patients with history of, or current admission for kidney transplantation
9. Patients with comfort measures only orders (*i.e.*, CMO)
10. Moribund not expected to survive  $>24$  hours
11. Confirmed pregnancy
12. Patients treated with extracorporeal membrane oxygenation (ECMO), ventricular assist device (VAD), or intra-aortic balloon pump (IABP)
13. Organ donors with neurological determination of death (*i.e.*, brain dead donors)
14. Drug overdose requiring CKRT for drug clearance
15. Enrollment in a concurrent interventional clinical trial with direct impact on fluid balance (*e.g.*,  $>500$  mL study drug administration)

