#### 4.2.3 RECRUITMENT RATE

A successful recruitment rate will be defined as achieving an enrollment rate of 2 patients per month per center during the trial. The recruitment metric will be calculated as the mean number (standard deviation) of recruited patients per active screening month.

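### The SAP describes a different, apparently earlier, design from the protocol, with a different separation threshold and a recruitment rule that can reverse that primary verdict at the planned enrolment

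*SAP*

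**What the plan says.** The SAP summarises a trial "among 144 critically ill patients with AKI treated with CKRT in 6 ICUs"; the protocol, one "among 112 critically ill patients with AKI treated with CKRT in 10 ICUs across two hospital systems". For the lead-in, the SAP has "During the first five months, all ICUs will continue with a liberal" strategy and protocol 6.3.2 has "During the first six months of data collection, all sites will continue with a liberal" strategy. Recruitment succeeds in SAP 4.2.3 by "achieving an enrollment rate of 2 patients per month per center during the trial" and in protocol 5.8.1 by "achieving an enrollment rate of 1 patient per ICU per time window during the trial". SAP 3.2 has a "Body Mass Index" exclusion that the protocol lacks.

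| Item | SAP | Protocol |
|---|---|---|
| ICUs, patients | 6 (3 + 3), 144 (sections 3, 3.6) | 10 (5 + 5), at most 112 (sections 3, 4, 6.1) |
| All-liberal lead-in | 5 months (3) | 6 months (3, 6.3.2) |
| Step | every 3 months (3) | every 2 months or at 10 patients, whichever is first (6.3.2) |
| Separation, mL/kg/h | 0.52, both criterion and test null (3, 4.2.1) | 0.53 (3, 4, 5.8.1); 0.5 in the rationale of 5.8.1; 0.53-0.57 in 9.1 |
| Recruitment success | 2 per month per center (3, 4.2.3) | 1 per ICU per time window (3, 4, 5.8.1) |
| BMI exclusion | >40 (3.2) | none (6.6) |
| Prior net fluid removal excluded | >24 h (3.2) | >48 h (6.6) |
| Respiratory distress excluded | any patient (3.2) | un-intubated only (6.6) |
| Allocation table | six sequences, steps 0 to 6 (5.4.3) | ten ICUs to cross over (6.3.2) |

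Protocol section 9 gives no analysis model and refers to the SAP. The two agree on the detailed definition of a protocol deviation (protocol 5.8.1, SAP 4.2.2), SD 0.75, ICC 0.01, two-sided alpha 0.05, 80% power and intention-to-treat.

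**The concern.** Neither text is an amendment log; both read as operative. Because the protocol hands the analysis over, this SAP is the only place an analyst can look for methods, and it also carries thresholds and a design that the protocol does not share. Two of the three primary feasibility outcomes, separation and recruitment, have different success figures in the two documents. If the difference is left until data are in, choosing which document governs becomes a post hoc choice of verdict, and this trial's purpose is to decide whether a larger one is feasible.

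**Working it through.** **1. Are these slips of the pen or two designs?** I used the Hussey-Hughes stepped-wedge variance with a random ICU intercept, fixed period effects, equal cells and a normal approximation. Let I be ICUs, T periods, n patients per cell, s² = SD²(1 − ICC)/n and t² = SD² × ICC. With X the 0/1 treatment indicator, U is its total, W the sum of squared period totals and V the sum of squared ICU totals. Then

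Var = I·s²(s² + T·t²) / [(IU − W)s² + (U² + ITU − TW − IV)t²].

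Inputs from both documents: SD² = 0.5625, so t² = 0.005625 and SD²(1 − ICC) = 0.556875.

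- *SAP, 6 × 7, N = 126:* n = 3, s² = 0.185625, U = 21, W = V = 91. Var = 0.25059/7.28438 = 0.03440, SE 0.185. Detectable difference 2.80 × 0.185 = 0.520; power at 0.52 is 0.801. The SAP's figure reproduces.
- *Protocol, 10 × 11, N = 111:* n = 1.009, s² = 0.55186, U = 55, W = V = 385. Var = 3.3869/96.625 = 0.03505, SE 0.187. Detectable difference 0.525; power at 0.53 is 0.808. The protocol's figure reproduces too.

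Each document is therefore coherent with its own, different grid.

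**2. Which is earlier?** The protocol keeps traces of the SAP's design. Section 5.2.8 refers to 144 patients in six ICUs over 30 months. Section 6.6.2 limits screening to less than 24 hours of net fluid removal. Section 6.6.1 numbers pregnancy as criterion 11 and ECMO as 12, which fits the SAP's list; in the protocol's own list they are 10 and 11.

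**3. Recruitment over 24 months.** Protocol 6.1 and 9.1 give the 24 months. I read 'center' as a hospital system, since the SAP calls the trial two-center.

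- SAP rule: 2 centers × 2 × 24 = 96 patients.
- Protocol rule with two-month windows throughout (the reading that protocol 9.1 supports): 10 ICUs × 12 windows × 1 = 120 patients.
- Planned 112: 112/24/2 = 2.33 per center-month, which passes the SAP; 112/120 = 0.93 per ICU-window, which fails the protocol.
- On this reading the verdicts conflict for any total from 96 to 119.

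**4. The same with the lead-in as one window.** The protocol does not define the window.

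- Six-month lead-in plus (24 − 6)/2 = 9 steps is 10 windows. The rule needs 100, and 112/100 = 1.12 passes. The conflict shrinks to 96-99.
- Lead-in plus 10 steps is the 11-period grid of step 1. The rule needs 110, and 112/110 = 1.02 passes. At two months per step this lasts 6 + 20 = 26 months, when the SAP rule needs 2 × 2 × 26 = 104, so the conflict is 104-109. If the 10-patient trigger compressed it into 24 months, the conflict would be 96-109.

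**5. The protocol's own arithmetic.** Section 9.1 plans 0.93 per ICU per two months: 0.93 × 10 × 12 = 111.6. It then equates 1 per ICU per two months with 112, but 1 × 10 × 12 = 120. On the 12-window reading the planning rate is below the success criterion, and 112 is a maximum.

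**6. Separation and power.** The separation verdict differs only for an estimate from 0.52 to below 0.53, a band of 0.01 mL/kg/h. Putting the SAP's 0.52 into the protocol's grid gives 0.52/0.187 − 1.96 = 0.82, a power of about 0.79 against 0.808.

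**The case against.** The strongest reply is that the recruitment reversal depends on a reading the protocol does not fix. Step 4 shows that two sensible ways of counting windows let 112 pass both rules, and the 10-patient trigger can shorten windows further. That stands: it would be too strong to say that the same data must give opposite conclusions. The 12-window reading still has direct support in protocol 9.1, and some range of totals conflicts under every reading. If 'center' meant an ICU, the SAP rule would need 10 × 2 × 24 = 480 and the conflict would run the other way.

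Part of the trouble also lies inside the protocol (112 against 120; 0.5, 0.53 and 0.53-0.57), so correcting the SAP alone would not settle the verdict. That stands too.

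A reader might infer three further things that the documents do not support:

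- *That protocol-eligible patients would be dropped from the intention-to-treat set.* The eligibility wording of that set is in protocol 2.2, so it naturally means protocol eligibility. SAP 4.4 calls incorrect enrolment a rare threat but gives no rule for removing anyone.
- *That the SAP fixes six sequences and seven periods in the model.* SAP 5.4.3 is a reporting shell. The model in SAP 4.1 names ICU and time effects without counting them, and runs unchanged on ten ICUs.
- *That the trial is wrongly powered because of the mismatch.* Step 6 shows almost no change.

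**Conclusion.** The concern holds in this form: the SAP states a different design, a different separation null and a different primary recruitment criterion from the protocol. That it is the earlier design is an inference. The SAP is dated 9/20/2022 and the protocol text available carries no date, but the traces in protocol 5.2.8, 6.6.1 and 6.6.2 make it likely. The need to align the two does not depend on the order.

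The material effect is on recruitment. With 24 months' accrual and 'center' as hospital system, 112 patients pass the SAP and fail the protocol under two-month windows throughout; they pass both if the lead-in is one window. The separation effect is confined to 0.52 to below 0.53. The deviation outcome, the power and the GLMM form are essentially untouched. Because a primary success figure differs and correction is cheap, this should be settled before any analysis.

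**What to change.** Before analysis:

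1. Reissue the SAP on the current design: 10 ICUs, 112 patients, six-month lead-in, a step every two months or at 10 patients, and a 10-sequence allocation table. State the period grid used for the time effect.
2. Reconcile the SAP's eligibility list with the protocol's on BMI, prior net fluid removal and respiratory distress, and correct the leftover text in protocol 5.2.8, 6.6.1 and 6.6.2 to match.
3. Put one separation threshold in both documents, as criterion and as test null, reconciling 0.5, 0.53 and 0.53-0.57 in protocol 5.8.1 and 9.1.
4. Put one recruitment criterion in both. Define the time window, including how the lead-in and a step triggered by 10 patients count, and say whether a center is a hospital system. Reconcile 112 with 10 × 12 = 120 so that the criterion can be met at the planned enrolment.

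The cost is one SAP revision and a small protocol clarification, with no effect on patients.
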